11.2 Specific analyses for Pharmaceuticals and Medical Devices Agency (PMDA)

The following endpoints will be summarized for participants in Japan only:

- Study participant characteristics, including important PDs (as specified in [Section 5](#))
- Demographics and other baseline characteristics, including medical history, prior and concomitant medications (as specified in [Section 6](#))
- Study IMP duration and number of infusions (as specified in [Section 8.1](#))
- Use of rescue medication (IVIg, PEX) due to worsening (as specified in [Section 9.1.4](#))
- MG-ADL total score and change from Baseline (as specified in [Section 9.1.1](#))
- TEAE Summaries (as specified in [Section 8.2.2](#))
 - TEAE overview
 - The number, percentage of participants and frequency of the following TEAEs will be summarized by SOC, HLT, PT, and by most recent dose prior to onset of TEAEs and RLZ total
 - Any TEAEs
 - Any TEAEs by maximum intensity (mild, moderate and severe)
 - Any TEAEs by relationship
 - Serious TEAE
 - Participant discontinuation due to TEAEs
 - Permanent withdrawal of IMP due to TEAEs
- ADA summaries (as specified in [Section 10.3.2](#)):
 - Number and percentage of participants with positive, negative, missing or inconclusive sample ADA status at the time of each visit and RLZ total will be summarized by treatment group and RLZ total.
 - Number and percentage of participants in each of the ADA classifications presented in [Table 10-1](#) will be summarized by treatment group and RLZ total.

11.3 Headache questionnaire

The results of the headache questionnaire will be listed for each study participant using ES. No summary tabulations will be provided for these assessments.

11.4 Myasthenia Gravis Foundation of America (MGFA) by Visit

The results of MGFA by visit will be listed for each study participant using RS. No summary tabulations will be provided for these assessments.

13 APPENDICES

13.1 Quantitative Myasthenia Gravis scale

The QMG scale comprises 13 items, including ocular and facial movement, swallowing, speech, limb strength and forced vital capacity. Scoring for each item ranges from no weakness (0) to severe weakness (3), with an overall score range from 0 to 39, ie, a higher score indicates more severe disease. A 3-point change in the overall score is considered to be clinically relevant.

The QMG testing form is provided in [Table 13–1](#). The total score is obtained by summing the responses to each individual item.

[REDACTED]
[REDACTED] The score ranges from 0 to 33.

In the event of missing data, the following rules will be applied:

[figure not shown]
- If 1 or 2 items are not answered, the overall score will be obtained by imputing the missing items with the average score across the remaining items at the specific visit. The imputed value will be rounded to one decimal place
- If more than 2 items are missing the overall score will not be calculated at the specific visit

Table 13–1: Quantitative myasthenia gravis testing form

Item	None	Mild	Moderate	Severe
Grade	0	1	2	3

[REDACTED]

Item	None	Mild	Moderate	Severe
Grade	0	1	2	3

F=female; M=male.

13.2 Myasthenia Gravis-Composite scale

The MG-C score items and associated scores are provided in [Table 13–2](#).

The MG-C score comprises 10 items, each of which is weighted differently in the calculation of the overall score. The overall score ranges from 0 to 50, with a higher score indicating more severe disease.

The total score is obtained by summing the responses to each individual item.

[figure not shown]

[figure not shown]
The score ranges from 0 to 41.

In the event of missing data at a particular visit, the MG-C score will not be calculated. Due to the different weighting applied to each item it is not possible to impute the missing data with the average score across the remaining items.

Table 13–2: MG-C score items and scoring algorithm

Item	Result/Grade	Result/Grade	Result/Grade	Result/Grade
------	--------------	--------------	--------------	--------------

^a Moderate weakness for head and neck items should be construed as weakness that equals roughly 50%+/-15% of expected normal strength. Any weakness milder than that would be mild and any weakness more severe than that would be classified as severe.

13.3 Myasthenia Gravis-Activities of Daily Living

The MG-ADL score comprises 8 items, each with a score of 0 to 3. The total score is obtained by summing the responses to each individual item. Thus, the score ranges from 0 to 24 with a higher score indicating more disability. The MG-ADL testing form is provided in [Table 13-3](#). The total score is obtained by summing the responses to each individual item. Thus, the score ranges from 0 to 24.

In the event of missing data, the following rules will be applied:

- If 1 or 2 items are not answered, the overall score will be obtained by imputing the missing items with the average score across the remaining items at the specific visit. The imputed value will be rounded to one decimal place
- If more than 2 items are missing the overall score will not be calculated.

Table 13–3: MG-Activities of Daily Living

13.4 Myasthenia Gravis Symptoms PRO

The MG Symptoms PRO instrument consists of 42 items across 5 scales: ocular symptoms (items 1 to 5); bulbar symptoms (items 6 to 15); respiratory symptoms (items 16 to 18); physical fatigability (items 19 to 33) and muscle weakness fatigability (items 34 to 42).

The MG Symptoms PRO calculation includes two steps: 1) rescoring the item responses; and 2) calculation of the final scores. Details of the scoring is found in the Myasthenia Gravis Symptoms PRO Instrument Scoring Manual dated 28 February 2019.

Step 1: Rescoring the item responses. The item responses should be rescored so as the lowest item-level score is 0. Rescoring rules are provided in [Table 13-4](#), [Table 13-5](#), and [Table 13-6](#).

Step 2: Calculation of the MG Symptoms PRO Scores

- MG Symptom PRO scale scores

The MG symptom PRO scale scores are calculated using the formula below, i.e. the sum of item scores is linearly transformed to have all domain scores ranging from 0 to 100:

$$\begin{aligned} & \text{MG Symptom PRO scale score} \\ &= \frac{\text{Sum of item scores within the scale}}{\text{Raw score range}} \\ & \times \frac{\text{Total number of items in the scale}}{\text{Number of non missing items in the scale}} \times 100 \end{aligned}$$

The score for each scale is calculated only when at least 70% of the items are completed. Details on the minimum number of items needed for score calculation and the range of raw score are provided in [Table 13-7](#).

Table 13-4: MG Symptoms: Ocular, Bulbar, and Respiratory Symptoms Rescoring

[figure not shown]

Table 13-4: MG Symptoms: Ocular, Bulbar, and Respiratory Symptoms Rescoring

[figure not shown]
[figure not shown]
A large black rectangular redaction box covers the entire content of Table 13-4.

Table 13-5: MG Symptoms: Physical Fatigue Rescoring

A large black rectangular redaction box covers the entire content of Table 13-5.

[figure not shown]

Table 13-6: MG Symptoms: Muscle Weakness Fatigability

The content of Table 13-6 is completely redacted with a large black box. The table structure, including headers and data rows, is not visible.

[figure not shown]

Table 13-7: Description of the MG Symptoms PRO Scale Scores

13.5 Myasthenia Gravis Impairment Index

The MG-II is provided in [Table 13-8](#). The MGII can be summarized as a total score and also as 2 sub-scores reflecting an Ocular and a Generalized domain.

The total score is the raw sum of all the items, including the clinical examination and the patient-reported questionnaire.

The ocular score is calculated by summing 8 items reflecting ocular impairments. These items are: patient questionnaire items 1 to 6 and examination items 1 and 2.

The generalized score is calculated by adding items 7 to 22 from the patient questionnaire and items 3 to 6 from the examination.

In the event of missing data, the following rules will be applied:

- In the case where at least 7 of the 8 items from the Ocular subscale are answered, the Ocular subscale score will be generated after imputing the missing response by the average of non-missing responses, by adding all item scores. If there are 2 or more missing data out of the 8 Ocular subscale items, then the Ocular subscale score will be missing.
- In the case where at least 18 of the 20 items from the Generalized subscale are answered, the Generalized subscale score will be generated after imputing the missing response(s) by the average of non-missing responses, by adding all item scores. If there are 3 or more missing data out of the 20 Generalized subscale items, then the Generalized subscale score will be missing.
- In the case where both the Ocular and the Generalized subscale scores are non-missing, then the Total score will be calculated as the sum of the Ocular and the Generalized subscale scores. If one of the two subscale scores are missing, then the Total score will be missing.

PUBLIC COPY
This document cannot be used to support any marketing authorization application and any extensions or variations thereof.

Table 13-8: MG Impairment Index

[figure not shown]

Table 13-8: MG Impairment Index

[figure not shown]

Table 13-8: MG Impairment Index

[figure not shown]

Table 13-8: MG Impairment Index

[figure not shown]
[figure not shown]

Table 13-8: MG Impairment Index

This document is confidential and intended solely for the individual named. If you have received this document by mistake, please notify the individual named immediately by email at [redacted] or by phone at [redacted].

13.6 MG-QOL15r

The MG-QOL15r is a brief survey, completed by the study participant, that is designed to assess some aspects of "quality of life" related to MG. The total score is calculated by summing all 15 individual items.

In the event of missing data, the following rules will be applied:

- In the case where at least 70% of the items (i.e. 11 items out of the 15) are answered, the total score will be generated after imputing the missing responses by the average of available (ie non-missing) responses, by adding all item scores.
- In the case where more than 30% (i.e. 5 items or more) are missing, the total score will not be generated.

This document cannot be used to support any marketing authorization application and any extensions or variations thereof.

PUBLIC COPY

Table 13-9: MG-QOL15r

Please indicate how true each statement has been (over the past few weeks).	Not at all	Somewhat	Very much
	0	1	2
1. I am frustrated by my MG			
2. I have trouble using my eyes because of my MG (e.g. double vision)			
3. I have trouble eating because of MG			
4. I have limited my social activity because of my MG			
5. My MG limits my ability to enjoy hobbies and fun activities			
6. I have trouble meeting the needs of my family because of my MG			
7. I have to make plans around my MG			
8. I am bothered by limitations in performing my work (include work at home) because of my MG			
9. I have difficulty speaking due to MG			
10. I have lost some personal independence because of my MG (e.g. driving, shopping, running errands)			
11. I am depressed about my MG			
12. I have trouble walking due to MG			
13. I have trouble getting around public places because of my MG			
14. I feel overwhelmed by my MG			
15. I have trouble performing my personal grooming needs due to MG			

MG-QOL15r
 Muscle and Nerve 2016 Doc;34(6):1015-1022.

Total MG-QOL15r score

MG-QOL15r - United States/English.
 MG-QOL15r_AU1.0_eng-USor.doc

13.7 Markedly abnormal laboratory and diagnostic criteria for Rozanolixizumab program

The following criteria will be applied in the determination of marked abnormalities for laboratory assessment values. They are based on Version 5 of the Common Terminology Criteria for Adverse Events (CTCAE) grade 3 or higher criteria unless otherwise noted. If both high and low criteria are shown for a parameter, the criteria should be summarized separately in tabular or graphical data summaries.

Table 13-10: Hematology

Parameter	Unit (conventional)	Unit (standard)	Marked Abnormality Criteria
Hemoglobin	g/dL	g/L	<8.0 g/dL, <80 g/L
WBC (Leukocytes) ¹	10 ⁹ /L	10 ⁹ /L	Low: <2.0 x 10 ⁹ /L High: >30 x 10 ⁹ /L
Lymphocytes Absolute	10 ⁹ /L	10 ⁹ /L	Low: <0.5 x 10 ⁹ /L High: >20 x 10 ⁹ /L
Neutrophils Absolute	10 ⁹ /L	10 ⁹ /L	<1.0 x 10 ⁹ /L
Platelets	10 ⁹ /L	10 ⁹ /L	<50.0 x 10 ⁹ /L

¹WBC (Leukocytes) markedly abnormal high criterion is not based on Version 5 CTCAE Grade 3 or higher criteria. Due to the mechanism of action of RLZ, the safety alert is related to infection risk which would be identified by a lower cut-point than the standard which is related to acute leukemias. A markedly abnormal high cut-point >30 x 10⁹/L is applied to flag leukocytosis (George 2012).

Table 13-11: Chemistry

Parameter	Unit (conventional)	Unit (standard)	Marked Abnormality Criteria
AST (SGOT)	U/L	U/L	>5.0 x ULN
ALT (SGPT)	U/L	U/L	>5.0 x ULN
ALP (Alkaline Phosphatase)	U/L	U/L	>5.0 x ULN
GGT (Gamma Glutamyl Transferase)	U/L	U/L	>5.0 x ULN
Bilirubin (Total)	mg/dL	umol/L	>3.0 x ULN if Baseline value is normal; >3.0 x Baseline value if Baseline is abnormal
Albumin	g/dL	g/L	<2 g/dL; <20 g/L
Creatinine	mg/dL	umol/L	>3.0 x ULN
Estimate glomerular filtrate rate (eGFR) ¹	mL/min/1.73 m ²	mL/min/1.73 m ²	eGFR <29 mL/min/1.73 m ²

C reactive protein (CRP) ²	mg/L	mg/L	>10 mg/L
Calcium ³	mg/dL	mmol/L	Low: Corrected serum calcium of <7.0 mg/dL; <1.75 mmol/L
			High: Corrected serum calcium of >12.5 mg/dL; >3.1 mmol/L
Immunoglobulin G ⁴	(g/L)	(g/L)	≤1 g/L
Potassium	mmol/L	mmol/L	Low: <2.5 mmol/L
			High: >6.0 mmol/L
Sodium	mmol/L	mmol/L	Low: <125 mmol/L
			High: >155 mmol/L
Glucose ⁵	mg/dL	mmol/L	Low: <40 mg/dL; <2.2 mmol/L
			High: >250 mg/dL; >13.9 mmol/L
Total Cholesterol	mg/dL	mmol/L	>400 /dl; >10.34 mmol/L
Triglycerides	mg/dL	mmol/L	>500 mg/dl; >5.7 mmol/L

Abbreviations: ALT= alanine aminotransferase; AST = aspartate aminotransferase; dL = deciliter; GGT: gamma-glutamyltransferase; L = liter; mg = milligram; mmol = millimoles; µg = microgram; U = unit; ULN = upper limit of normal

Note: Marked abnormality criteria are defined by Grade 3 or higher events according to the Common Terminology for Adverse Events (CTCAE), Version 5.0, November 17, 2017 unless otherwise noted.

¹eGFR is calculated using the Chronic Kidney Disease Epidemiology Collaboration or CKD-EPI formula (https://qxmd.com/calculate/calculator_251/egfr-using-ckd-epi) which is $eGFR = 141 * \min(\text{Scr}/\kappa, 1)^\alpha * \max(\text{Scr}/\kappa, 1)^{-1.209} * 0.993^{\text{Age}} * 1.018$ [if female] * 1.159 [if black]; where Scr is serum creatinine (mg/dL), κ is 0.7 for females and 0.9 for males, α is -0.329 for females and -0.411 for males, min indicates the minimum of Scr/ κ or 1, and max indicates the maximum of Scr/ κ or 1. For derivation from values in standard units (umol/L) the κ values are 61.88 for females and 79.56 for males.

²Includes CRP and High Sensitivity (HS) CRP. Reference for marked abnormality criteria: Nehring, S.M.; Goyal, A.; Patel, B.C. (2020). StatPearls Publishing. web link: <https://www.ncbi.nlm.nih.gov/books/NBK441843/>.

³Corrected Calcium (mmol/L) = 0.02 * (40 – Albumin (g/L)) + Calcium (mmol/L).

⁴Immunoglobulin G criterion based on immunodeficiency literature and noted in RLZ study protocols.

⁵Glucose high criterion defined by Grade 3 and higher events according to CTCAE, Version 4.03, June 14, 2010.

Table 13-12: Vital Signs

Parameter	Abnormality Criteria
Pulse Rate (beats/minute)	≤50 and a decrease from Baseline of ≥15 ≥120 and an increase from Baseline of ≥15
Systolic Blood Pressure (mmHg)	≤ 90 and a decrease from Baseline of ≥20 ≥ 180 and an increase from Baseline of ≥20
Diastolic Blood Pressure (mmHg)	≤50 and a decrease from Baseline of ≥15 ≥105 and an increase from Baseline of ≥ 15
Temperature	>101 °F (38.3 °C)

Parameter	Abnormality Criteria
Body Weight	$\geq 10\%$ decrease from Baseline $\geq 10\%$ increase from Baseline

Table 13-13: Electrocardiogram

Parameter	Abnormality Criteria
QT interval (ms)	≥ 500 ms
	≥ 60 ms increase from Baseline
QTc(F) (ms)	≥ 500 ms
	≥ 60 ms increase from Baseline
PR interval (ms)	Treatment-emergent value >200 ms
QRS interval (ms)	Treatment-emergent value >100 ms
Heart rate (bpm)	<50 bpm
	>120 bpm

Abbreviations: bpm = beats per minute; ms = milliseconds; QTc(F) = Fridericia corrected QT interval;
 Note: Treatment-emergent is defined as meeting the criteria at any post-Baseline visit after the first infusion of study medication and within 56-days of the last infusion and not meeting the same criteria during Baseline

13.8 AEs of focus for Rozanolixizumab program

The AEOF selection criteria is specified in the Rozanolixizumab Safety AEs of Focus document developed by UCB. The purpose of this document is to detail the approach to identifying TEAEs meeting criteria for AEOF for the Rozanolixizumab (also called RLZ) program.

Following Events are AEOFs for Rozanolixizumab for MG studies:

No	Event (also included in Title of TFL output)	Selection criteria
1	Headache (Note: also included in AESM if severe)	TEAE with HLT='Headaches'
2	Gastrointestinal disturbances (Note: also included in AESM if severe)	TEAE with HLT='Gastrointestinal and abdominal pains (excl oral and throat)' or HLT='Gastrointestinal signs and symptoms NEC' or HLT='Nausea and vomiting symptoms' or HLT='Diarrhoea (excl infective)' or HLT='Gastritis (excl infective)'
3	Hypersensitivity reactions	SMQ='Hypersensitivity'
4	Anaphylactic reactions	SMQ='Anaphylactic reaction' and

		
TEAEs that either emerged on the same day as when a study medication injection reaction was received, or that emerged one day after a study medication injection was received, and which fulfill any of the following 3 criteria should be included in the summary table:
 
 1. If a subject reports any TEAE which codes to a PT included in Category A, then the event will be flagged as an anaphylactic reaction. 2. If a subject reports any TEAE which codes to a PT included in Category B AND reports any TEAE which codes to a PT included in Category C, and both TEAEs have the same start date, then both events will be flagged as anaphylactic reactions. 3. If a subject reports any TEAE which codes to a PT included in Category D AND reports (either a TEAE which codes to a PT included in Category B OR a TEAE which codes to a PT included in Category C), and both TEAEs have the same start date, then both events will be flagged as anaphylactic reactions.
5	Injection site reactions	TEAE with HLT='Injection site reactions' or HLT='Infusion site reactions' or HLT='Administration site reactions NEC'
6	Infusion Reactions	Infusion reaction marked on AE CRF page (based on the assessment by the Investigator)
7	Infections	TEAE with SOC ="Infections and infestations" Note: This was added as a reminder for safety that infections are considered as AE of focus and require assessment. No programming of this topic is required as TEAEs can be found in general AE Tables.
8	Opportunistic infections (Note: also included in AESM)	Opportunistic infections (including tuberculosis) will be summarized in a stand-alone table using UCB-defined search criteria. Opportunistic infections are identified in two steps using the attached spreadsheet for MedDRA v24.0 in UCB Rozimab Safety AEs of Focus document: Step 1: Refer to column B of the spreadsheet which identifies the Preferred Terms (PTs) to be classified as opportunistic infections using either a single 'x' or a double 'xx'.

		
• TEAEs which code to a PT flagged with a single 'x' need to also be serious in order to be considered an opportunistic infection.• All TEAEs which code to a PT flagged with a double 'xx' are considered to be an opportunistic infection, regardless of seriousness. 
All serious TEAEs in the study database which code to a PT flagged with a single 'x' and all TEAEs in the study database which code to a PT flagged with a double 'xx' will be summarized as an opportunistic infection in the stand-alone table. [CQ97NAM= 'Opportunistic Infection - Automatic']
 
Step 2: Refer to column C of the spreadsheet which identifies the PTs that need to be evaluated on a case-by-case basis by the study physician and safety physician in order to determine whether it is a true opportunistic infection or not. The process for physician review is as follows:
 
1. Study programming team creates a spreadsheet which lists all of the subjects with a TEAE present in the database which codes to a PT identified as case-by-case. [CQ98NAM= Opportunistic Infection - Manual Review Candidate] Information from the AE dataset to be included in the spreadsheet: Subject ID, AE verbatim term, System Organ Class (SOC), High Level Term (HLT), Lower Level Term (LLT), PT, AE start date, AE end date, seriousness, severity, relationship to study medication, action taken. Additionally, a column will be included where the study physician/safety physician can document their decision on the case.2. Study physician/safety physician (SPs) reviews the cases in the spreadsheet separately and reconciles final decision, and indicates in the additional column which AEs are confirmed to be opportunistic infections via a single 'x'.3. Study programming team incorporates these decisions into the AE dataset by merging the SPs decisions for individual subjects / PTs and flagging both the automatic and the confirmed opportunistic infections as such in the dataset. [CQ99NAM= 'Opportunistic Infection – Adjudicated']
--	--	---

		
The SPs reviews the context of all of a subject's data (AEs and possibly other) and concludes individually. Indicators of relevant cases may be e.g. repetitive occurrences, conjunction of other events or findings considered relevant.
 
All subjects with a case-by-case PT reported that has been confirmed by the SPs to be an OI will be summarized as such in the stand-alone table, along with all of the events identified in Step 1 of this process. [CQ99NAM= 'Opportunistic Infection – Adjudicated']
 
The timing and frequency of Step 2 should be outlined and agreed to by the study team at the beginning of the study. It is suggested that this process be executed multiple times throughout the course of the study, more frequently in the weeks leading up to database lock, and one final time immediately prior to database lock.
 
Following the initial review of case-by-case events, subsequent reviews will be based on the cumulative set of case-by-case events present in the database at each time point of spreadsheet creation.
 
Physician decisions from previous runs should be retained in each subsequent run. The final run of the spreadsheet, with all SP decisions on the full set of case-by-case events, will be archived at the conclusion of the study analysis prepared for agency submission.

9	Reductions in albumin and plasma proteins	TEAEs with PT='Blood albumin decreased' or PT='Protein albumin ratio' or LLT='Plasma protein abnormal' or LLT='Proteins serum plasma low'
10	Effects on the kidney	TEAEs in SMQ= 'Acute renal failure'
11	Drug related hepatic disorders	TEAEs in SMQ='Drug related hepatic disorders - comprehensive search'
12	Effect on lipids	TEAEs with PT= 'Blood cholesterol increased' or PT= 'Low density lipoprotein increased' or PT= 'Blood triglycerides increased' or PT= 'Hypercholesterolaemia' or PT= 'Hypertriglyceridaemia' or PT= 'Hyperlipidaemia' or PT= 'Dyslipidaemia' or PT= 'Lipids increased'

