- Bodyweight \geq 100kg: dose to be administered [REDACTED]

If one of the doses described above is determined to be futile and is discontinued after the interim analysis in MG0003 or MGC003, then that dose arm will be dropped from MG0004 as well, and study participants in the affected dose arm will be transferred to the continuing dose arm. If both dose arms are used in MG0004, study participants will be allowed to switch dose arms for tolerability and efficacy reasons at the discretion of the Investigator (see Section 6.6).

In MG0004, rozanolixizumab will be administered SC on a [REDACTED] basis over a 52-week Treatment Period. Weekly visits will be either on-site or at home, as described in the Schedule of Activities (Section 1.3). During the first 4 weeks, the weekly visits will be on-site. From Weeks 5 to 8, on-site visits and at home visits will occur on an alternating basis. From Weeks 9 to 48, study participants will have 1 site visit every 4 weeks, such that 1 site visit will be followed by 3 home visits, unless the study participant chooses to complete the scheduled at-home assessments at the site. Weeks 49 to 51 will then involve 1 site visit followed by 2 home visits. At the end of the 52-week Treatment Period in MG0004, study participants will participate in an 8-week Observation Period.

In exceptional circumstances (eg, pandemic, hurricanes, etc) where study-specific investigations may not be conducted according to study protocol, contingency measures will be in place (see Section 8).

This OLE study will be replaced by MG0007, an OLE study with [REDACTED] based on MG worsening. Upon study site approval of MG0007, as well as fulfilment of regulatory requirements, study participants will have the opportunity to rollover directly into MG0007 and will no longer have the opportunity to rollover to MG0004. In the event a study participant has

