8.2.3 Adverse events of focus

Rozanolixizumab adverse events of focus (AEOF) include the following categories:

- Headaches
- Gastrointestinal disturbances
- Hypersensitivity reactions
- Anaphylactic reactions
- Injection site reaction
- Infusion reaction
- Infections
- Opportunistic infections
- Reductions in albumin and plasma proteins
- Effects on the kidney
- Drug related hepatic disorders
- Effects on lipids

1. The number and percentage of study participants who experience each category of the AEOF will be summarized by most recent dose level prior to onset of the AEOF and RLZ total treatment group. The following summaries will be presented by SOC, HLT, and PT:

- AEOF
- Serious AEOF
- AEOF by relationship
- AEOF by maximum intensity (mild, moderate and severe)

2. Additionally, the summaries for the AEOF headache and gastrointestinal disturbances in Treatment Period by intensity will be presented separately by most recent dose level and RLZ total.

3. Graphs for AEOF headache in Treatment Period by time of onset (relative to infusion), severity, causality and duration for each study participant will also be provided.

A by-subject listing of all AEOF by category (as listed above) will be provided by treatment group and participant. Most recent dose will be presented in listing even when the AE start date is partial. Further details related to the statistical analysis of the above mentioned treatment-emergent AEOFs are provided in [Section 13.8](#).

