10.3.2 ADA summaries

The following outputs will be presented on the SS.

Tables:

- Number and percentage of participants with ADA (positive, negative, inconclusive, missing) and NAb (positive, negative, missing) sample status at the time of each visit will be summarized by first dose received and RLZ total. Denominator is the number of study participants having a non-missing result at that visit.
- Number and percentage of participants in each of the individual and combined ADA participant status categories presented in [Table 10-1](#) will be summarized by first dose received and RLZ total at each scheduled visit and EOS visit. The table will be repeated by prior treatment in MG0003 (RLZ total or placebo) up to Week 9.

- Total prevalence of pre-existing ADA and NAb, defined as number and percentage of participants having an ADA positive sample status at baseline, with the denominator being the total number of study participants having an evaluable sample result at baseline. Missing samples will not be included in the denominator. The table will be repeated by prior treatment in MG0003 (RLZ or placebo). The same will be repeated for NAb.
- The first occurrence of treatment-emergent ADA positivity: cumulative number and percentage of TE-ADA positive participants (category 7) who are ADA positive for the first time at each visit. The table will be repeated by prior treatment in MG0003 (RLZ or placebo).
- Summary table of mean maximum percentage CFB in total IgG and mean CFB in MG-ADL, summarized by ADA participant categories 1, 2, 9, 10, 11 and 12 for the corresponding time period of interest and by treatment group and RLZ total [REDACTED].
- Overall summary table of TEAEs at Week 9 and EOS summarized by ADA participant categories 1, 2, 7 and 8 for the corresponding time period of interest.
- Summary of incidence of TEAE at Week 9 and EOS by ADA participant category 1, 2, 7 and 8 for the corresponding time period of interest.
- Summary table of AEOF hypersensitivity reactions, anaphylactic reactions and infusion reactions at Week 9 and EOS by ADA participant category 1, 2, 7 and 8 for the corresponding time period of interest.

Figures:

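### SAP 13.8 ties the same-day limb of the anaphylaxis window to an injection reaction rather than the injection, so read literally it drops dosing-day events with no reaction recorded and admits some later ones

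*SAP*

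**What the plan says.** SAP 8.2.3 lists "Anaphylactic reactions" among the adverse events of focus (AEOF). SAP 13.8, row 4, gives the selection rule. A TEAE must belong to the anaphylactic-reaction SMQ, fall inside a timing window, and satisfy any one "of the following 3 criteria should be included in the summary table". Those criteria combine the SMQ's Categories A to D.

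The timing window has two limbs:

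- Same day: "TEAEs that either emerged on the same day as when a study medication injection reaction was received".
- Next day: "or that emerged one day after a study medication injection was received".

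Row 4 does not define an injection reaction. The nearest entries in the same table are row 5, injection site reactions chosen by MedDRA high level term, and row 6, infusion reactions, defined as "Infusion reaction marked on AE CRF page (based on the assessment by the Investigator").

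The flag feeds two sets of outputs. SAP 8.2.3 states: "The number and percentage of study participants who experience each category of the AEOF will be summarized by most recent dose level". It adds versions for serious events, by relationship and by maximum intensity, and a listing by category. SAP 10.3.2 plans a "Summary table of AEOF hypersensitivity reactions, anaphylactic reactions and infusion reactions at Week 9 and EOS", split by ADA participant category.

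**The concern.** The two limbs should describe one window around a dose: the day of dosing and the day after. As printed, they hang on different things. The first needs a reaction on that day; the second needs only a dose on the previous day. The rule is therefore stricter on the dosing day than on the day after.

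That is the wrong way round for this event. The anaphylaxis criteria in Protocol 10.22 describe onset within minutes to hours, so dosing-day events are the ones the table most needs to hold. Protocol 10.3.3 also asks investigators to record a diagnosis, where possible, in place of its component signs and symptoms. A site that reports anaphylaxis may therefore enter no other reaction term.

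Safety is the primary objective, and Protocol 2.3 names infusion and hypersensitivity reactions as a potential risk. The tables of adverse events of special monitoring (AESMs) give no fallback, because Protocol 8.3.7 states that anaphylaxis is not classed as one and the SAP 8.2.2 list omits it.

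**Working it through.** The plan gives no figure to reproduce, so the check applies the rule as a logical condition to each possible case.

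**Inputs**

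- Both limbs of the window: SAP 13.8, row 4. The window and a category criterion are both required.
- Visit spacing: Protocol 4.1 says "Weekly visits will be either on-site or at home". Table 1-1 allows 2 days either side of each visit. The dosing interval is redacted, so dosing at these visits is an assumption.

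**Step 1: can the next-day limb rescue a dosing-day event?** It could only if there had also been a dose the day before. With visits 7 days apart and each within its window, the shortest gap between two visits after Visit 1 is 7 − 2 − 2 = 3 days. Under the dosing assumption there is normally no dose the day before, so no rescue.

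**Step 2: apply the rule to a TEAE that already meets the SMQ and a category criterion.** Compare the rule as printed with the same rule after *reaction* is removed.

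| Day of onset | Reaction recorded or marked that day? | As printed | *Reaction* removed |
|---|---|---|---|
| Dosing day | No | Excluded | Included |
| Dosing day | Yes | Included | Included |
| Day after dosing | No | Included | Included |
| Day after dosing | Yes | Included | Included |
| Later non-dosing day | No | Excluded | Excluded |
| Later non-dosing day | Yes | Included | Excluded |

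**Step 3: read the result.** Two of the six cells change, in opposite directions. The printed wording leaves out a dosing-day event with no reaction recorded, and lets in an event well after dosing if a reaction is recorded that day.

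**Step 4: which wording was intended?** A dose is received; a reaction is not. The second limb uses the same verb with the injection as its object. Both facts point to *reaction* as a stray word. No other supplied section of the SAP restates the window.

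**The case against.** The strongest reply is that this is a typing slip that a competent programmer would read through, because the sentence makes sense only without the extra word. SAP 13.8 also says that the criteria come from the sponsor's AEs of Focus document, which may be worded correctly and may be what is programmed from. Both points are fair, and they keep this a minor correction. They do not remove it. SAP section 1 sets out to supply everything needed for the analyses, and *injection reaction* looks like a real term beside rows 5 and 6, so a literal implementation is possible.

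A second reply concerns what counts as a recorded reaction. Row 6 relies on a mark on the AE page, not on a second AE term. If the investigator marks the anaphylaxis record itself as an infusion reaction, that record could be argued to satisfy the same-day limb alone. Protocol Table 10-4 handles infusion reactions and anaphylaxis together, so this is plausible. It stands: only events with neither a recorded nor a marked reaction are at risk.

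A third reply is that a dropped event is not lost to the report. It stays in the general TEAE tables and listings, and in the serious, severe or withdrawal tables where it qualifies (SAP 8.2.2). It may also appear under hypersensitivity, row 3, which has no timing window. This stands too.

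A reader might still infer that a large share of anaphylaxis would be missed. For example, assume that 80–90% of cases start on the infusion day and that 50–100% of those have no separate reaction term. Then 0.8 × 0.5 = 40% and 0.9 × 1.0 = 90%. The documents support neither input. The second also asks about a separate term when a mark may be enough. If every such event were marked, the loss would be 0.8 × 0 = 0%. A range of 0–90% carries no information.

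**Conclusion.** The rule is wrong as printed, very probably because of one stray word. Taken literally, it misclassifies in two ways: dosing-day events that meet the category criteria but have no reaction recorded or marked are excluded, and events on later non-dosing days that coincide with a reaction are included.

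The effect is confined to the anaphylactic-reaction AEOF outputs and the AEOF table by ADA category. Its size cannot be estimated from the documents. No inference changes, because the SAP plans no statistical testing (4.1) and all analyses are descriptive (4.6).

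The exclusion rests on two assumptions: that the program follows the printed text, and that dosing takes place at the weekly visits. Whether the AEs of Focus document contains the same wording is unknown. The documents do not show that any case has been or will be missed, or that the tighter same-day condition was a deliberate choice.

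**What to change.** Reword the window in SAP 13.8, row 4, so that both limbs refer to the same thing: *TEAEs that started on the same day as, or one day after, a study medication infusion*. Using *infusion* also matches the route in Protocol Table 6-1, where the drug is a solution for subcutaneous infusion. Keep the SMQ condition and the three category criteria unchanged.

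Then confirm that the analysis program and the sponsor's AEs of Focus document use the same window. The cost is a one-line SAP correction and that check. No new data or analyses are needed.
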